### 7.1.2 Serious Adverse Event (SAE) -Immediately Reportable to the Sponsor

A serious adverse event is any adverse event that meets any of the following criteria:

- Fatal (i.e., the adverse event actually causes or leads to death)
- Life threatening (i.e., the adverse event, in the view of the investigator, places the subject at immediate risk of death). This does not include any adverse event that, had it occurred in a more severe form or was allowed to continue, might have caused death.
- Requires or prolongs inpatient hospitalization
- Results in persistent or significant disability/incapacity (i.e., the adverse event results in substantial disruption of the subject’s ability to conduct normal life functions)
- Congenital anomaly/birth defect in a neonate/infant born to a mother exposed to study drug
- Significant medical event in the investigator's judgment (e.g., may jeopardize the subject or may require medical/surgical intervention to prevent one of the outcomes listed above).

### 7.1.3 Severity

A clinical determination will be made of the severity of an adverse event. The terms “severe” and “serious” are not synonymous. Severity is a description of the intensity of the manifestation of the AE and is distinct from seriousness, which implies a subject outcome. Severity will be assessed according to the US National Cancer Institute (NCI) Common Terminology Criteria for Adverse Events (CTCAE) scale (Table 8):

**Table 8: NIH Common Criteria for Adverse Events (CTCAE) Scale †**

AE Severity	Description
Grade 1	Mild; asymptomatic or mild symptoms; clinical or diagnostic observations only; intervention not indicated
Grade 2	Moderate; minimal, local or noninvasive intervention indicated; age-appropriate instrumental ADL*
Grade 3	Severe or medically significant but not immediately life-threatening; hospitalization or prolongation of hospitalization indicated; disabling; limiting self-care ADL**.
Grade 4	Life-threatening; urgent intervention indicated.
Grade 5	Death related to AE

† Common Terminology Criteria for Adverse Events (CTCAE), version 4.03. National Cancer Institute. US Department of Health and Human Services. June 14, 2010. Available at: [http://evs.nci.nih.gov/ftp1/CTCAE/CTCAE\\_4.03\\_2010-06-14\\_QuickReference\\_5x7.pdf](http://evs.nci.nih.gov/ftp1/CTCAE/CTCAE_4.03_2010-06-14_QuickReference_5x7.pdf)

\*Instrumental activities of daily living (ADL) examples include preparing meals, shopping for groceries or clothes, using the telephone, managing money, etc.

\*\* Self-care ADL includes to bathing, dressing and undressing, feeding self, using the toilet, and taking medications and does not include being bedridden.

## 7.2 Relationship of Adverse Event to the IMP

A determination will be made of the relationship between an adverse event and the IMP. A causal relationship is present if a determination is made that there is a *reasonable possibility* that the adverse event may have been caused by the IMP. In general, a causal relationship will be assigned when evidence exists to support the causal relationship. As there is no prescribed treatment intervention in this study, relationship would be extrapolated backwards to dosing in protocol MSB-GVHD001.

When assessing a potential relationship between the IMP and an AE, the following parameters should be considered:

- Temporal relationship between IMP and/or protocol-specified procedures and the AE.
- The biological plausibility that the IMP caused the event
- Any underlying/concurrent illness in the subject
- Concomitant medications the subject may have received
- How commonly the event occurs in the study population, independent of treatment.

## 7.3 Relationship to Study Procedure

For each adverse event, the relationship to the IMP delivery procedure must be recorded as either **related** (there is reasonable possibility of a causal relationship between the event and the study procedure) or **not related** (there is no reasonable possibility of a causal relationship between the event and the study procedure).

## 8. REPORTING ADVERSE EVENTS AND SERIOUS ADVERSE EVENTS

Any adverse event (AE) occurring after a subject has signed the informed consent (or randomization, as appropriate) should be recorded on the appropriate CRF page.

Any SAE (as described in [Section 7.1.2](#)) occurring after a subject has signed the informed consent should be immediately reported to the sponsor or designee within 24 hours of the investigator's knowledge of the event. All subjects with an SAE must be followed up and the outcomes reported until the event is resolved or has stabilized.

Upon occurrence of an SAE, the investigator must:

- Immediately notify the sponsor's designee, Quintiles Lifecycle Safety. SAE reporting will originate in the electronic data capture (EDC) system and an email will be sent to

individuals with designated responsibility for safety. The paper SAE form is in place as a back-up in the rare event that EDC is not accessible to the reporter of the SAE:

- [REDACTED]
- Provide copy of all relevant source documents, including concomitant medications, as appropriate.

All SAEs that are considered unexpected and related to the study product will be reported by the Sponsor or its designee as a 15-day report to the Regulatory Authorities *as applicable* and to all participating investigators.

SAEs that are considered unexpected, related to the study and are life threatening, or result in death will be reported by the Sponsor or its designee to the appropriate Regulatory Authorities and to all participating investigators as a 7-day report.

Each investigator must notify the IRB/EC responsible for reviewing the study at their site of all 15-day or 7-day safety reports required by local regulations or IRB/EC requirements and shall provide the Sponsor or its designee with written confirmation of said IRB/EC notification.

### **8.1 Procedures for Reporting Pregnancies**

All pregnancies that occur during the study are to be reported immediately to the individual identified in the General Information page of this protocol, and the investigator must provide Sponsor or designee, by facsimile, a Pregnancy Tracking Form. Pregnancies in female partners of male subjects are **not** required to be followed up. All subjects who become pregnant will be monitored to the completion or termination of the pregnancy, including perinatal and neonatal outcome. Monitoring of the subject should continue until conclusion of the pregnancy. If the pregnancy is associated with an SAE (e.g. hemorrhage, spontaneous abortion), then in addition to the Pregnancy Form, a separate SAE form must be provided as described in [Section 8](#).

### **8.2 Laboratory Test Abnormalities**

Laboratory test results will appear on laboratory reports that are submitted directly from the central laboratory. Local laboratory results, if applicable, should be recorded on the CRF.

Any abnormal laboratory result that is clinically significant should be recorded as a single diagnosis in the CRF. An abnormal laboratory result is considered to be clinically significant if it meets one or more of the following conditions:

- Is accompanied by clinical symptoms.
- Requires change in concomitant therapy (e.g. addition of, interruption of, discontinuation of, or any other change in a concomitant medication, therapy or treatment).

These conditions will apply to any protocol- and non-protocol- specified safety laboratory results from tests performed after ICF signature that fall outside the laboratory reference range and are considered clinically significant. These conditions will not apply to any abnormal laboratory results that are outside the laboratory reference range, yet does not meet the criteria for clinical significance; these latter results will be analyzed and reported as laboratory abnormalities. In the event of clinically significant abnormal laboratory test values, the tests should be repeated and followed up until they have returned to the normal range and/or the abnormality is adequately explained or accounted for. If an acceptable explanation is established, it should be recorded on the CRF.

### **8.3 Expedited Reporting to Health Authorities, Investigators, Institutional Review Boards, and Ethics Committees**

The Sponsor will promptly evaluate all adverse events against cumulative product experience to quickly identify and communicate possible new safety findings to investigators, IRBs, IECs, and applicable health authorities based on applicable legislation.

To determine reporting requirements for single adverse event cases, the Sponsor will assess the expectedness of these events using the following reference documents:

- IMP IB
- IMP Development Core Safety Information (DCSI) Document, if applicable.

The Sponsor will compare the severity of each event and the cumulative event frequency reported for the study with the severity and frequency reported in the applicable reference document.

Reporting requirements will also be based on the Investigator's assessment of causality and seriousness, with a provision for upgrading by the Sponsor as needed.

## 9. STATISTICAL CONSIDERATIONS AND ANALYTICAL PLAN

### 9.1 Statistical Analysis Plan

Since this is an extension trial of MSB-GVHD001, data presented for MSB-GVHD002 will be presented in two ways:

1. For the extension period only. This will include assessments beyond Day 100.
2. For the entire period spanning both MSB-GVHD001 and MSB-GVHD002 trials.  
In particular, this includes time-to-event data (flares and therapy escalation), survival data, incidence of cGVHD, and frequency of flares.

Categorical variables will be summarized using frequencies and percentages. Continuous variables will be summarized using descriptive statistics (n, mean, standard deviation [SD], median, minimum, and maximum). Confidence intervals, if presented, will have a two-sided 95% confidence level. For time-to-event variables, Kaplan-Meier curves will be presented as appropriate.

In general, the baseline value for a variable is defined as the last non-missing observation prior to or equal to the first dose date of study treatment in MSB-GVHD001. Baseline for analyses of the entire period of MSB-GVHD001 and MSB-GVHD002 will be the same as baseline defined for Protocol MSB-GVHD001. The baseline for the extension period beyond Day 100 will be the same values at the end of study/Day 100 for MSB-GVHD001. Data collected at unscheduled time points will not be summarized at the unscheduled time points.

The actual day relative to start of treatment will be determined from the first dose date in Protocol MSB-GVHD001, which will be considered 'Study Day 0'. Study day will be calculated from the first infusion date in Protocol MSB-GVHD001. A detailed statistical analysis plan (SAP) will be finalized prior to the database lock.

### 9.2 Analysis Population

The analysis population for safety in this study, the Safety Population, will include all subjects who received at least one dose of the study treatment in study MSB-GVHD001 and entered into study MSB-GVHD002. The population to be evaluated for duration of response will include all subjects who participated in Protocol MSB-GVHD001, received the first 8 doses of remestemcel-L as outlined in that protocol, and showed overall response (OR) or very good partial response (VGPR) to remestemcel-L at Day 28.

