
Study Design This is a safety follow-up study through 180 days of remestemcel-L treatment in subjects who participated in MSB-GVHD001. This study will also explore duration of response over time. Subjects who participated in MSB-GVHD001 and received at least one dose of remestemcel-L as outlined in that protocol will be evaluated at baseline (Day 100) and at Days 120, 140, 160 and 180 for safety endpoints. Subjects who participated in Protocol MSB-GVHD001 and received the first 8 doses of remestemcel-L as outlined in that protocol will be evaluated at baseline (Day 100) and at Days 120, 140, 160 and 180 after initial remestemcel-L infusion for evidence of duration of response over time.

Study Population Safety population: All subjects who participated in Protocol MSB-GVHD001 and received at least one remestemcel-L infusion in that protocol.
 
Duration of response population: All subjects who participated in Protocol MSB-GVHD001, received the first 8 doses of remestemcel-L as outlined in that protocol, and showed overall response (OR) or very good partial response (VGPR) to remestemcel-L at Day 28.

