**Assessments**

**Primary Endpoints**

Safety through 180 days of remestemcel-L treatment in subjects who participated in Protocol MSB-GVHD001 and received at least one infusion of remestemcel-L.

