**Safety**

1. Adverse events
2. Serious adverse events
3. Survival through Day 180
4. Ectopic tissue formation

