### Analysis Populations

The analysis population for the safety assessment in this study will include all subjects from Protocol MSB-GVHD001 who have signed the Informed Consent form and have received at least one dose of remestemcel-L. The analysis population for the duration of response assessments in this study will include Protocol MSB-GVHD001 subjects with overall response and VGPR to remestemcel-L at Day 28, who have signed the Informed Consent form and have completed treatment for the first 28 days, as prescribed in Protocol MSB-GVHD001.

[figure not shown]

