### **2.3 Rationale for Subject Population**

This study will explore duration of response and evaluate the safety of remestemcel-L in pediatric subjects with aGVHD that has failed to respond to first-line systemic steroid treatment who participated in MSB-GVHD001. The safety population will be comprised of any subject who received at least one infusion of remestemcel-L in MSB-GVHD001. Survival at Day 180 will be evaluated. Additionally, duration of response will be explored in subjects who completed initial therapy of remestemcel-L (first 8 doses) in MSB-GVHD001 and responded to therapy, in order to best assess the impact of a response to treatment of aGVHD.

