**Table 6: Schedule of Assessments and Procedures**

	Baseline/ Visit 1	Visit 2	Visit	Visit 4	Visit 5	
Study Days	Day 100 (same as Day 100 in MSB-GVHD001)	Day 120	Day 140	Day 160	End of Study/ Day 180	
Visit window	±7 days	±5 days	±5 days	±5 days	±7 days	Unscheduled
Inclusion/exclusion criteria/informed consent a	X					
Vital signs (HR, BP, Temp, RR, oxygen saturation) b		X	X	X	X	X
Height and weight					X	X
Physical examination		X	X	X	X	X
CMV c		X	X	X	X	X
Hematology laboratory tests				X	X	X
Chemistry laboratory tests				X	X	X
Urinalysis				X	X	X
Hospitalization d						X
Acute GVHD assessment (Skin, Lower GI, Upper GI, Liver)						
Acute GVHD assessment (Skin, Lower GI, Upper GI, Liver)		X	X	X	X	X
Chronic GVHD assessment						
Chronic GVHD assessment		X	X	X	X	X
Concomitant medicationf						
Concomitant medication f		X	X	X	X	X
Transfusiong						
Transfusion g						X
Optional CT scan or MRI (Chest, Abdomen and Pelvis)l						
Optional CT scan or MRI (Chest, Abdomen and Pelvis) l					X	X
12-Lead ECG						
12-Lead ECG					X	X
Termination/end of study						
Termination/end of study					X	X
Pregnancy testl						
Pregnancy test l					X	X
Adverse event evaluationk						
Adverse event evaluation k		X	X	X	X	X

a Informed consent for MSB-GVHD002 may be provided to the subject simultaneously with the informed consent for MSB-GVHD001, or at any visit prior to Day 180 (± 7 days) .

b Vital signs include measurements of heart rate (HR), blood pressure (BP), respiratory rate (RR), and temperature (temp).

c Investigators should provide standard of care treatment for viral infections as appropriate, including prophylaxis and treatment if there is evidence of viral reactivation and/or infection

d Hospitalization with a start date after the visit window of Day 100 (Day 107) will be collected in MSB-GVDH002.

Hospitalization with a start date before the visit window of Day 100 (Day 106) will be collected in MSB-GVDH001.

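### Section 9.2 limits the Safety Population to subjects who entered MSB-GVHD002 while other sections use all dosed subjects; applied to the Day 180 survival summary in 9.4.2, the limit drops deaths before entry

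*Combined protocol and SAP*

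**What the plan says.** Three places point to all dosed subjects:

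- Synopsis, Study Population: "All subjects who participated in Protocol MSB-GVHD001 and received at least one remestemcel-L infusion in that protocol".
- Section 2.3: "The safety population will be comprised of any subject who received at least one infusion of remestemcel-L in MSB-GVHD001".
- Synopsis, Primary Endpoints, repeated in section 4.1.1: safety through 180 days "in subjects who participated in Protocol MSB-GVHD001 and received at least one infusion of remestemcel-L". One of the four safety parameters listed is "Survival through Day 180".

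Two places add a condition:

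- Section 9.2: the Safety Population "will include all subjects who received at least one dose of the study treatment in study MSB-GVHD001 and entered into study MSB-GVHD002".
- Synopsis, Analysis Populations: "all subjects from Protocol MSB-GVHD001 who have signed the Informed Consent form and have received at least one dose of remestemcel-L". It does not say which study's form.

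On entry, section 5.1 enrols MSB-GVHD001 subjects who meet the MSB-GVHD002 criteria but gives no date. Table 6 marks the row "Inclusion/exclusion criteria/informed consent" at Day 100, but its footnote a says that consent "may be provided to the subject simultaneously with the informed consent for MSB-GVHD001, or at any visit prior to Day 180" (±7 days). Sections 6.1 and 6.3 allow consent up through Day 180 (±7 days). Section 6.3 foresees late ethics approval, has the affected Day 100 to Day 160 visits marked as missed, and starts MSB-GVHD002 data collection at consent.

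Section 9.4.2 counts subjects alive, dead, lost or withdrawn from Day 0 to Day 180. It times survival from transplant, aGVHD onset or treatment initiation, and censors survivors at last contact. It names no analysis population and has no rule for delayed entry.

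**The concern.** Section 9.4.2 stands under Safety Data Analysis, so a programmer would ordinarily apply the Safety Population of 9.2. A child must be alive to enter MSB-GVHD002. If the set is limited to entrants but the clock starts at first infusion or earlier, each late entrant brings a stretch of follow-up in which death was impossible by construction. Children who died in that stretch without entering are absent from the count.

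The result would carry the label of survival from first infusion in treated children, but would in part be survival given that the child lived to enter. Survival through Day 180 is one of four primary safety parameters. The primary objective is descriptive, so what is at stake is a misread survival figure, not a false test result.

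**Working it through.** **Comparing the texts.** The sentence in 9.2 on the duration-of-response set carries no entry condition, while the sentence on safety does, so the safety condition reads as a deliberate restriction. The consent form in the synopsis (Analysis Populations) is probably the MSB-GVHD002 form: that paragraph defines sets for this study, and written consent is inclusion criterion 2 in section 5.2.1. It then selects much the same children as 9.2. That leaves one operative conflict: dosed, against dosed and entered.

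**Does another section settle it?** Section 9.1 lists survival data among the analyses spanning both trials, and the 9.4.2 table starts at Day 0. Both fix the time window. Neither says who is counted, and a Day 0 window on an entrants-only set is exactly the problem.

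**Size, as an illustration.** The plan gives no sample size, expected survival or consent timing to reproduce. Inputs:

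- One-year survival s = 5% or 30%, the background range for steroid non-responders in section 1.2. Treating it as timed from first infusion is an assumption.
- Constant hazard (assumption), so S(t) = s^(t/365).
- Entry shares and days (assumptions), with entry timing unrelated to prognosis.

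Survival in all dosed subjects:

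- s = 0.30: S(100) = 0.7190 and S(180) = 0.5523.
- s = 0.05: S(100) = 0.4401 and S(180) = 0.2282.

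If a share p enters by Day 0 and the rest enter on day d if still alive, the entered set is the fraction p + (1 − p)·S(d) of those dosed. Everyone alive at Day 180 is in it, so reported survival is S(180) / [p + (1 − p)·S(d)].

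- Half enter at Day 100, s = 0.30: 0.5523 / (0.5 + 0.5 × 0.7190) = 64.3%.
- Half enter at Day 100, s = 0.05: 0.2282 / (0.5 + 0.5 × 0.4401) = 31.7%.
- All enter at Day 100: 0.5523 / 0.7190 = 76.8%, and 0.2282 / 0.4401 = 51.9%.
- All enter at Day 160: S(180)/S(160) = s^(20/365) = 93.6% and 84.9%.

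| Entry pattern | s = 5% | s = 30% |
|---|---|---|
| All by Day 0 (true value) | 22.8% | 55.2% |
| Half by Day 0, half at Day 100 if alive | 31.7% (+8.9 points) | 64.3% (+9.0) |
| All at Day 100 if alive | 51.9% (+29.0) | 76.8% (+21.6) |
| All at Day 160 if alive | 84.9% (+62.0) | 93.6% (+38.4) |

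**The case against.** The strongest reply is that the plan already points to all dosed subjects for this endpoint. The primary endpoint statements say so, section 9.1 puts survival in the whole-period analyses, and 9.4.2 starts at Day 0. No sentence applies the 9.2 set to 9.4.2. This stands to the extent that the bias is a risk under one reading, not a stated feature of the plan. It does not remove the conflict, because the section that formally defines the Safety Population says something else and 9.4.2 does not choose.

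A second reply is that the figures are not trial data. That is right: the survival range is background, the constant hazard and entry shares are assumed, and nothing suggests that half or all of the children enter late. Also, 9.4.2 asks for counts and survival times; percentages follow only from the general rule in 9.1. The table shows direction and scale, not a forecast.

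Two stronger readings are tempting and do not hold:

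- A reader might infer three distinct safety populations. The synopsis consent form and entry in 9.2 plausibly pick the same children, and section 4.1.1 states an endpoint rather than defining a population.
- A reader might infer from Table 6 that entry is always Visit 1 at Day 100, so that the bias is the same whatever the consent timing. Written consent is itself an inclusion criterion and may come after Day 100. A child who consents at Day 160 cannot have met the criteria at Day 100, and the same model then gives 84.9% to 93.6%, not 51.9% to 76.8%.

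**Conclusion.** The concern holds as one conflict: all dosed subjects in the synopsis (Study Population), section 2.3 and the primary endpoint statements, against dosed and entered subjects in section 9.2 and probably in the synopsis (Analysis Populations). Applying 9.2 to the survival summary in 9.4.2 overstates Day 180 survival when children enter after Day 0 and earlier deaths without entry are left out. The bias is zero if all consent at or before first infusion and consent counts as entry. It grows with the share of late entrants and the lateness of entry. Under the stated assumptions it is about 9 points if half enter at Day 100 and 22 to 29 points if all do. The actual size cannot be found from the documents, which do not give consent timing. The documents do not show that the sponsor intends the restricted set for 9.4.2, only that they leave it open. It should be fixed before the SAP is final. This point covers only the primary safety parameter in 9.4.2.

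**What to change.** 1. Make section 9.2 and the synopsis (Analysis Populations) agree with the synopsis (Study Population) and section 2.3: all subjects with at least one infusion in MSB-GVHD001.
2. In 9.4.2, name that set for survival from Day 0 to Day 180. Count deaths during MSB-GVHD001, and censor non-entrants at last contact; the existing censoring rule covers this once the set is named.
3. Define entry as the date of MSB-GVHD002 consent, and say in the synopsis which form is meant wherever consent is still a condition. Keep the entered set for summaries of the extension period beyond Day 100 only.
4. Report the numbers of non-entrants and late entrants. Exclusion criterion 1 leaves participation partly to the investigator's judgement, so non-entry may be related to prognosis.

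The cost is a few sentences in the synopsis, 9.2 and 9.4.2, plus a count in the disposition table. Section 9.1 leaves the detailed SAP open until before database lock. Delayed-entry modelling is more than this defect needs. There are three downsides. Reported survival may look less favourable. Deaths of non-entrants after their last parent-study contact stay unknown. The change also assumes that the MSB-GVHD001 consent, which was not supplied, allows parent-study data on non-entrants to be used.
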